6.6. Unscheduled Visits

Unscheduled study visits may occur at any time medically warranted. Any assessments performed at those visits should be recorded in the eCRF.

If the subject develops new areas of AD, treatment of the new areas may begin after documenting of the new EASI score and photography of the new or expanding areas. This may occur at an unscheduled visit.

7. CONDUCT OF STUDY ASSESSMENTS AND PROCEDURES

7.1. Administration of Informed Consent Form

Valid informed consent must be obtained from the study subject before conducting any study-specific procedures using an ICF approved by the local IRB/IEC that contains all elements required by ICH E6 and describes the nature, scope, and possible consequences of the study in a form understandable to the study subject. Local and institutional guidelines for ICF content and administration must be followed; the original signed ICF must be retained by the investigator, and a copy of the signed ICF must be provided to the study subject. The informed consent process for each subject must be documented in writing within the subject source documentation.

7.2. Interactive Response Technology Procedure

The IRT will be contacted to obtain a subject ID number when a subject enters screening. Upon determining that the subject is eligible for study entry, the IRT will be contacted to obtain the treatment assignment. Additionally, the IRT will be contacted at each regular study visit to update the study drug supply. Full details will be provided in the IRT manual.

7.3. Demography and Medical History

7.3.1. Demographics and General Medical History

Demographic data and general medical history will be collected at screening.

7.3.2. Disease Characteristics and Treatment History

A disease-targeted medical and medication history will be collected at screening.

7.4. Prior and Concomitant Medications and Procedures

Prior and concomitant medications and procedures will be reviewed to determine subject eligibility. All concomitant medications and measures must be recorded in the eCRF, and any medication received or procedure performed within 30 days before randomization and up to the end of study will be recorded in the eCRF. The medication record will be maintained after signing the ICF to document concomitant medications, including any changes to the dose or regimen. Concomitant medications include any prescription, over-the-counter, or natural/herbal preparations taken or administered during the study period. Concomitant treatments and/or procedures that are required to manage a subject's medical condition during the study will also be recorded in the eCRF.

7.5. Safety Assessments

7.5.1. Adverse Events

Adverse events will be monitored from the time the subject signs the ICF. Subjects will be instructed to report all AEs during the study and will be assessed for the occurrence of AEs throughout the study. In order to avoid bias in eliciting AEs, subjects will be asked general, nonleading questions such as "How are you feeling?" All AEs (serious and nonserious) must be recorded on the source documents and eCRFs regardless of the assumption of a causal relationship with the study drug. The definition, reporting, and recording requirements for AEs are described in [Section 8](#).

7.5.2. Physical Examinations

Physical examinations must be performed by a medically qualified individual such as a licensed physician, physician's assistant, or an advanced registered nurse practitioner, as local law permits.

Clinically notable abnormalities that are considered clinically significant in the judgement of the investigator are to be reported as AEs.

7.5.2.1. Comprehensive Physical Examination

The comprehensive physical examination will include height and body weight (at screening only) and assessment of the following organ or body systems: skin; head, eyes, ears, nose, and throat; thyroid; lungs; cardiovascular system; abdomen (liver, spleen); extremities; and lymph nodes; as well as a brief neurological examination.

7.5.2.2. Targeted Physical Examination

The targeted physical examination will be a symptom-directed evaluation. The targeted physical examination will include assessment of the body systems or organs, as indicated by subject symptoms, AEs, or other findings.

7.5.3. Vital Signs

Vital sign measurements include blood pressure, pulse, respiratory rate, and body temperature. Blood pressure and pulse will be taken with the subject in the sitting position after 5 minutes of rest. Clinically notable abnormalities that are considered clinically significant in the judgment of the investigator are to be reported as AEs.

7.5.4. Electrocardiograms

All 12-lead ECG will be performed with the subject in a recumbent or semirecumbent position after 5 minutes of rest.

The 12-lead ECGs will be interpreted by the investigator at the site to be used for immediate subject management. The decision to include or exclude a subject or withdraw a subject from the study based on an ECG flagged as "Abnormal, Clinically Significant" is the responsibility of the investigator, in consultation with the sponsor's medical monitor, as appropriate. Clinically notable abnormalities that are considered clinically significant in the judgment of the investigator are to be reported as AEs.

7.5.5. Laboratory Assessments

Clinical laboratory tests will be performed using a central laboratory. A detailed description of the procedures for sampling, handling, storage, and shipment of the central laboratory samples and all material such as test tubes and labels is provided in the central Laboratory Manual. If unscheduled local laboratory tests are performed, and if those results lead to a dose modification, delay, or dose interruption, or if any additional non-Protocol-required test is performed because of an AE, then those results and the normal reference ranges for those analytes must be documented in the eCRF. Otherwise, unscheduled local laboratory test results need not be entered in the eCRF.

Additional analytes may be requested based on emerging data, if indicated for safety of study subjects. In addition, some subjects may receive additional assessments as medically indicated; results of nonrequired tests may also be entered in the eCRF.

7.5.5.1. Chemistry

A panel of standard serum chemistries will be analyzed at times shown in [Table 2](#). A list of required analytes is found in [Table 3](#). All serum chemistries will be performed from blood samples collected without respect to food intake (ie, nonfasted).

7.5.5.2. Hematology

Hematology tests will be performed at each study visit indicated in [Table 2](#). A list of required analytes for scheduled visits is provided in [Table 3](#).

7.5.5.3. Urinalysis

Urinalysis will be performed at screening indicated in [Table 2](#).

7.5.5.4. Pregnancy Testing

Pregnancy testing will be performed on all female subjects as noted in the schedules of assessments ([Table 2](#)). Serum pregnancy test will be obtained at screening. A urine pregnancy test will be obtained all other visits. A positive urine pregnancy test should be confirmed by a serum pregnancy test.

7.5.5.5. Serology

Subjects will be tested for hepatitis and HIV as shown in [Table 3](#). Serology will be conducted during the screening period. This thorough hepatitis testing is being obtained to better interpret any abnormalities in liver function tests that may develop during the course of the study; therefore, it is not mandatory that results of all tests be available before enrollment (Day 1) if clinical evaluation and medical history provide no reason to suspect ongoing active or subclinical hepatitis infection.

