3. SUBJECT ELIGIBILITY

Deviations from eligibility criteria are not allowed because they can potentially jeopardize the scientific integrity of the study, regulatory acceptability, and/or subject safety. Therefore, adherence to the criteria as specified in the Protocol is essential.

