3.2. Subject Exclusion Criteria

A subject who meets any of the following criteria will be excluded from the study:

1. Subjects with evidence of acute acute or chronic infections.
2. Use of topical treatments for AD (other than bland emollients) within 2 weeks of baseline.
3. Systemic immunosuppressive or immunomodulating drugs (eg, oral or injectable corticosteroids, methotrexate, cyclosporine, mycophenolate mofetil, azathioprine) within 4 weeks or 5 half-lives of baseline (whichever is longer).
4. Subjects with other dermatologic disease besides AD whose presence or treatments could complicate the assessment of disease (eg, psoriasis).
5. Subjects with a history of other diseases besides dermatologic disorders (eg, other autoimmune diseases) taking treatments that could complicate assessments.
6. Subjects with cytopenias at screening, defined as:
 - a. Leukocytes $< 3.0 \times 10^9/L$.
 - b. Neutrophils $<$ lower limit of normal.
 - c. Hemoglobin $< 10 \text{ g/dL}$.
 - d. Lymphocytes $< 0.8 \times 10^9/L$.
 - e. Platelets $< 100 \times 10^9/L$.
7. Subjects with severely impaired liver function (Child-Pugh Class C) or end-stage renal disease on dialysis or at least 1 of the following:
 - a. Serum creatinine $> 1.5 \text{ mg/dL}$.
 - b. Alanine aminotransferase or AST $\geq 1.5 \times$ upper limit of normal (ULN).

8. Subjects taking potent systemic CYP3A4 inhibitors or fluconazole within 2 weeks or 5 half-lives, whichever is longer, before the baseline visit (topical agents with limited systemic availability are permitted, see [Appendix C](#)).
9. Subjects who have previously received JAK inhibitors, systemic or topical (eg, ruxolitinib, toficitinib, baricitinib, filgotinib, lestaurtinib, pacritinib).
10. Women who were pregnant or breastfeeding within 4 months before screening.
11. Current or recent history (< 30 days before screening and/or < 45 days before randomization) of a clinically meaningful bacterial, fungal, parasitic, or mycobacterial infection.
12. Positive serology test results for hepatitis B surface antigen or core antibody, or for hepatitis C virus antibody with detectable hepatitis C RNA at screening or human immunodeficiency virus (HIV) antibody.
13. Current clinically meaningful viral infection (eg, eczema herpeticum).

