5.1.2. Randomization and Blinding

For subjects who have met all study inclusion criteria and none of the exclusion criteria, the IRT should be contacted at baseline to obtain the study drug assignment.

The IRT system will set minimum entry criteria for an IGA score of 2 or 3, a BSA 3% to 20%, and will stratify the treatment groups based on baseline EASI score of ≤ 7 and > 7 . If 1 or both of the limits are reached, the IRT will stop assigning randomization numbers to that group, and no additional subjects will be enrolled in that group. Subjects, investigators, and the sponsor will remain blinded to each subject's treatment assignment throughout the study (with the exception of the unblinded team that will assess the results of interim analysis). Emergency unblinding will occur if an AE requires the investigator to be made aware of the subject's treatment assignment (see emergency unblinding procedures in [Section 8.4](#) and refer to the Study Reference Manual).

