6.1. Screening

Screening is the interval between the signing of the ICF and the day that the subject is enrolled in the study. Informed consent must be obtained before performing any study-specific procedures. Assessments that are required to demonstrate eligibility may be performed over the course of 1 or more days during screening.

Results from the screening evaluations will be reviewed to confirm subject eligibility before randomization or the administration of study drug. Tests with results that fail eligibility requirements may be repeated once during screening if the investigator believes the results to be in error. Additionally, a subject who fails screening may repeat the screening process 1 time if the investigator believes that there has been a change in eligibility status (eg, following recovery from an infection).

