6.2. Baseline

The results from the screening evaluations will be reviewed to determine whether the subject continues to meet the eligibility requirements as specified in the Protocol.

Subjects who have signed the ICF and meet all the entry criteria (see [Section 3](#)) may be enrolled or randomized in the study on Day 1.

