6.3. Treatment

Subjects who meet all of the study inclusion criteria and none of the exclusion criteria will return to the study site on Day 1 of administration. Dates for subsequent study visits will be determined based on this day and should occur within the visit windows outlined in the schedule of assessments ([Table 2](#)).

The treatment period begins when the subject receives their first dose of study drug, which will be administered in the clinic. The amount of study medication to be obtained from the pharmacy is determined by the BSA to be treated. On Day 1, the prescribed dose is to be determined by weighing a tube before and after the subject applies a thin film of study drug to the affected areas. For each 1% of BSA (palm with fingers) to be treated with study drug, approximately 2 inches (5 cm) of study drug may be used. Subjects will be advised to limit use to no more than 1 tube per application. Tubes of INCB018424 cream, triamcinolone 0.1% cream, or vehicle cream will be dispensed to subjects with detailed application instructions. The face and intertriginous areas may be treated with hydrocortisone 2.5% cream throughout the study.

For all study visits, subjects should apply the morning dose of study drug in the clinic to assess understanding of dispensing and application. A designated site staff member will be assigned to dispense and collect study drug, as well as instruct and assist with application of study drug during the clinic visits. This person should not have study responsibilities that involve either efficacy or safety assessments. Returned study drug should be collected before other study assessments being performed. Study drug should be dispensed at the end of the visit by the same designated staff, after other visit assessments have been completed. The subject should be counseled at this time regarding questions about dose or method of application.

Subjects who are noncompliant with study drug (defined as < 80% or > 120% compliant based on tube weight) will have the administration instructions reinforced by the investigator or a qualified designee. After reinforcement, subjects who again fail to meet < 80% or > 120% compliance benchmarks in a subsequent visit will be considered for withdrawal from the study. In such cases, the sponsor should be consulted by the investigator for instruction on the proper handling of the subject before withdrawal.

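### The serology section allows enrolment and first dosing before the hepatitis B and C results that decide exclusion criterion 12 are known

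*Protocol*

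**What the plan says.** Section 7.5.5.5 places hepatitis and HIV serology in the screening period. It explains the hepatitis tests as a later diagnostic aid: "This thorough hepatitis testing is being obtained to better interpret any abnormalities in liver function tests" that may arise during the study. From that reason it concludes that "it is not mandatory that results of all tests be available before enrollment (Day 1"), on condition that history and clinical evaluation give no ground to suspect active or subclinical hepatitis.

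Section 3.2, exclusion 12, gives the same tests a different role. It excludes anyone with "Positive serology test results for hepatitis B surface antigen or core antibody", with hepatitis C antibody and detectable RNA at screening, or with HIV antibody.

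Five other places in the Protocol require eligibility to be settled first:

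- Section 3: "Deviations from eligibility criteria are not allowed".
- Section 5.1.2: "For subjects who have met all study inclusion criteria and none of the exclusion criteria, the IRT should be contacted at baseline".
- Section 6.1: "Results from the screening evaluations will be reviewed to confirm subject eligibility before randomization or the administration of study drug".
- Section 6.2 reserves Day 1 enrolment or randomization for "Subjects who have signed the ICF and meet all the entry criteria".
- Section 6.3: "Subjects who meet all of the study inclusion criteria and none of the exclusion criteria will return to the study site" on Day 1, when the first dose is applied in the clinic.

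None of these makes an exception for serology.

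**The concern.** Section 7.5.5.5 treats hepatitis serology as background information that can arrive late. Exclusion 12 treats it as a laboratory condition of entry. A site that reads the serology section, which is the place to look for serology timing, finds express permission to enrol with results outstanding. Because dosing starts on Day 1, that permission covers exposure as well as registration.

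The stake is subject safety. The sponsor chose to keep people with these findings out of a trial in which four of six arms receive a JAK inhibitor, and in which subjects from any arm who qualify may receive the 1.5% cream twice daily after Week 8. The waiver lets that choice be bypassed for a subject whose infection nobody suspects. That subject would also remain in the ITT population, which includes everyone randomized. With so few subjects likely to be involved, no distortion of the efficacy results is argued.

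**Working it through.** The documents give no figure to reproduce. The check compares the texts and then bounds the number of subjects affected.

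**Step 1. Which hepatitis tests decide eligibility?** The list is from Protocol Table 3; the criterion is exclusion 12.

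| Hepatitis test in Table 3 | Decides exclusion 12? |
|---|---|
| Hepatitis B surface antigen | Yes |
| Hepatitis B core antibody | Yes |
| Hepatitis B core IgM antibody | Not named |
| Hepatitis C antibody | Yes, together with RNA |
| HCV-RNA (run only after a positive antibody) | Yes, together with antibody |

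Four of five decide eligibility. The waiver refers to the tests collectively and names none, so nothing confines it to core IgM. HCV-RNA depends on a prior positive antibody and so may be the last result to arrive.

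**Step 2. Can the waiver's condition stand in for the results?** The condition is a clinical judgement based on history and examination; exclusion 12 is a laboratory finding. The condition mentions subclinical infection, but history and examination cannot reliably detect that. A subject can satisfy the condition and still meet exclusion 12.

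**Step 3. What else would stop such a subject?**

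- IRT: the entry checks named in Section 5.1.2 are IGA and BSA. Serology is not named.
- Exclusion 7 removes subjects with ALT or AST at or above 1.5 × ULN. A subject with normal enzymes passes.
- Section 5.4.2 requires interruption when ALT or AST exceeds 3 × ULN. This acts only after exposure and only if enzymes rise.
- Section 5.5.1: once a disqualifying result arrives, withdrawal for failed eligibility is decided by the medical monitor with the investigator. It becomes mandatory only if the investigator judges that continuing would be injurious.

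**Step 4. Size.**

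Subjects randomized despite exclusion 12 = N × p × f, where

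- N = 300 (Section 4.3);
- p = proportion of otherwise eligible, clinically unsuspected subjects who would meet the hepatitis part of exclusion 12. Not in the documents; assumed 0.005 to 0.03;
- f = fraction randomized with a deciding result pending. Not in the documents; assumed 0.1, 0.5 or 1.0, the last being an upper bound.

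For the double-blind INCB018424 arms, multiply by 4/6 (equal allocation to six arms, four of them active cream).

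| f | 300 × p × f | × 4/6 |
|---|---|---|
| 0.1 | 300 × 0.005 × 0.1 = 0.15 to 300 × 0.03 × 0.1 = 0.9 | 0.1 to 0.6 |
| 0.5 | 300 × 0.005 × 0.5 = 0.75 to 300 × 0.03 × 0.5 = 4.5 | 0.5 to 3 |
| 1.0 | 300 × 0.005 × 1.0 = 1.5 to 300 × 0.03 × 1.0 = 9 | 1 to 6 |

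The last column leaves out open-label exposure after Week 8, which could reach subjects first assigned to vehicle or triamcinolone.

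**The case against.** The best defence is that the text can be read without conflict. The waiver says only that not every result must be back; it does not say that a result deciding exclusion 12 may be missing. Table 3 includes one test, core IgM, that exclusion 12 does not name, and five other sections require confirmed eligibility. A site that follows those sections would not randomize with exclusion 12 unresolved. This is a possible intention, but the limit to core IgM is not written anywhere and no order of precedence between sections is stated. The accurate description is therefore an internal contradiction: the protocol both forbids and permits the same act.

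Several objections concern size, and they have force:

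- Hepatitis C antibody without detectable RNA does not exclude, and the waiver and exclusion 7 remove subjects with clinical suspicion or raised enzymes. So p has to be read as what remains after those filters; using general seropositivity would overstate the count.
- Serology is a central-laboratory screening test and screening can last up to 28 days. If results usually return within that time, f is small and the 10% row is the more realistic one. Turnaround time is not given.

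On harm, the defence notes that the cream is topical, limited to 20% BSA and given for 8 weeks double-blind, with chemistry repeated at each treatment visit. These features limit the consequence but do not make an excluded subject eligible. The documents do not quantify a hepatitis risk for this cream, and none is claimed here.

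Whether the waiver reaches HIV is unclear. HIV appears in the section's opening sentence, but the waiver's reason and condition mention only hepatitis. Finally, the SAP cites three administrative changes and the Protocol refers to a laboratory manual. None was available, and any of them might give instructions on timing.

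**Conclusion.** The concern holds. As written, Section 7.5.5.5 permits Day 1 enrolment, and therefore first dosing, before results that decide exclusion 12 are known, in conflict with Sections 3, 3.2, 5.1.2, 6.1, 6.2 and 6.3. The clinical condition on the waiver narrows it but cannot replace a laboratory criterion, and the remaining safeguards miss a subject with normal liver enzymes.

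The count is likely to be small: below one subject if 10% have a result pending, and at most 9 (6 on INCB018424 in the double-blind period) at the top of both assumed ranges. Both p and f are assumptions. The conflict itself rests on the text alone and does not depend on them.

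**What to change.** Amend Section 7.5.5.5 so that hepatitis B surface antigen, hepatitis B core antibody, hepatitis C antibody (with reflex HCV-RNA if positive) and HIV antibody results must be available and reviewed before randomization. State that only the hepatitis B core IgM result may be pending on Day 1. Naming HIV removes the doubt about whether the waiver covers it.

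The cost is protocol wording and, at most, a short wait for results within the existing screening window of up to 28 days. All of these tests are already scheduled at screening, so no test or visit is added.

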7.6. Efficacy Assessments

7.6.1. Eczema Area and Severity Index Score

Atopic dermatitis will be assessed using the EASI scoring system ([Appendix B](#)), which is a validated disease measurement for clinical studies ([Hanifin et al 2001](#)). The severity strata for the EASI are as follows: 0 = clear; 0.1 to 1.0 = almost clear; 1.1 to 7.0 = mild; 7.1 to 21.0 = moderate; 21.1 to 50.0 = severe; 50.1 to 72.0 = very severe ([Leshem et al 2015](#)).

